#### 1.1.1.1.10 Definition of Overall Response Using irRC Will Be Based on the Following Criteria:

- Immune-related Complete Response (irCR): Complete disappearance of all tumor lesions (index and non-index), together with no new measurable or unmeasurable lesions, for at least 4 weeks from the date of documentation of irCR. All lymph nodes short axes must be < 10 mm.
- Immune-related Partial Response (irPR): The sum of the products of the 2 largest perpendicular diameters of all index lesions is measured and captured as the SPD baseline. At each subsequent tumor assessment, the sum of the products of the 2 largest perpendicular diameters of all index lesions and of new measurable lesions are added together to provide the Immune Response Sum of the Product of the Diameters (irSPD). A decrease, relative to baseline of the irSPD of 50% or greater is considered an irPR, in the absence of irCR. Must be confirmed no less than 4 weeks from the first irPR.
- **Immune-related Stable Disease (irSD):** irSD is defined as the failure to meet criteria for immune complete response or immune partial response, in the absence of progressive disease.
- Immune-related Progressive Disease (irPD): It is recommended in difficult cases (eg, increase in SPD or irSPD accompanied with significant individual lesion regression, "mixed response", or in presence of stable or improving performance status/clinical condition) to confirm PD at the following tumor assessment. Any of the following will

constitute progressive disease:

- At least 25% increase in the SPD of all index lesions over nadir SPD calculated for these lesions.
- At least a 25% increase in the SPD of all index lesions and new measurable lesions (irSPD) over the nadir SPD calculated for the index lesions.

Index Lesion Definition	Non Index Lesion Definition	New Measurable Lesions	New Unmeasurable Lesions	% Change in irSPD Tumor Burdon (including measurable new lesions when present)	Overall irRC Response
Complete Response	Complete Response	No	No	-100%	irCR
Partial Response	Any	Any	Any	$\leq -50\%$ >-50% to <+25% $\geq +25\%$	irPR irSD irPD
Stable Disease	Any	Any	Any	-50% to <+25% $\geq$ +25%	irSD irPD
Progressive Disease	Any	Any	Any	≥+25%	irPD

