# 11.1.4 Response Criteria

Response Criteria for Adult T-Cell Leukemia-Lymphoma									
Response	Definition	Lymph Nodes	Extranodal Masses	Spleen, Liver	Skin	Peripheral Blood	Bone Marrow		
Complete Remission 	Disappearance of all disease	Normal	Normal	Normal	Normal	Normal 	Normal		
Uncertified Complete Remission 	Stable residual mass in bulky lesion	$\geq 75\%$ decrease 	$\frac{>75\%}{\text{decrease}^3}$	No increase	≥50% decrease	$\geq 50\%$ decrease	Normal		
Partial Remission 	Regression of disease	$\geq 50\%$ decrease 	$\geq 50\%$ decrease 	No increase	$\geq 50\%$ decrease	$\geq 50\%$ decrease	Irrelevant		
Stable Disease 	Failure to attain complete/partial remission and no progressive disease	No change in size	No change in size	No change in size	No chance in size	No change	No change		
Relapse Disease or Progressive Disease	New or increased lesions	New or $\geq 50\%$ increase 	New or $\geq 50\%$ increase 	New or $\geq 50\%$ increase	New or $\geq 50\%$ increase	New or $\geq 50\%$ increase 	Re- appearance		
Not Assessable									

Require each criterion to be present for a period of at least 4 weeks

 Provided that <5% of flower cells remained, complete remission was judged to have been attained if the absolute lymphocyte count, including flower cells, was  $<4x10^{9}/L$ 

Calculate by the sum of the products of the greatest diameters of measurable disease

 Defined by  $\geq$  50% increase from nadir in the sum of the products of measurable disease

 Defined by  $\geq$ 50% increase from nadir in the count of flower cells and an absolute lymphocyte count, including flower cells, of >4x10^9/L

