#### 1.1.1.1.2 Measurable Lesions

Measurable lesions are lesions that can be accurately measured in 2 perpendicular diameters, with at least 1 diameter  $\ge 20$  mm and the other dimension  $\ge 10$  mm (10 mm x 10 mm for spiral CT with cuts of 5 mm). The area will be defined as the product of the largest diameter with its perpendicular.

Lymph nodes may also be considered measurable. To be considered pathologically enlarged and measurable, a lymph node must be at least 15 mm in short axis when assessed by CT scan (CT scan slice thickness recommended to be no greater than 5 mm).

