#### 1.1.1.1.3 Non-Measurable Lesions

Non-measurable (evaluable) lesions are all other lesions, including unidimensional measurable disease and small lesions (lesions without at least 1 diameter  $\geq 20$  mm, or pathological lymph nodes with short axis  $\leq 15$  mm), and any of the following: lesions occurring in a previously irradiated area (unless they are documented as new lesions since the completion of radiation therapy), bone lesions, leptomeningeal disease, ascites, pleural or pericardial effusion, lymphangitis cutis/pulmonis, abdominal masses that are not pathologically/cytologically confirmed and followed by imaging techniques and cystic lesions. Lymph nodes that have a short axis < 10 mm are considered non-pathological and should not be recorded or followed.

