#### 1.1.1.1.6 Calculation of Sum of Product of Diameters (SPD)

Sum of Product of Diameters is an estimate of tumor burden. The 2 greatest perpendicular diameters are used to estimate the size of each tumor lesion. The SPD is calculated as the sum of the product of the diameters for index tumor lesions. Several variations of the SPD are identified for the purpose of classification of tumor responses.

**SPD at Baseline**: The sum of the product of the diameters for all index lesions identified at baseline prior to treatment on Day 1.

**SPD at tumor assessment**: For every on-study tumor assessment collected per protocol or as clinically indicated, the SPD at tumor assessment will be calculated using tumor imaging scans. All index lesions and all new measurable lesions that have emerged after baseline will contribute to the SPD at tumor assessment (irSPD).

**SPD at NADIR:** For tumors that are assessed more than 1 time after baseline, the lowest value of the SPD (SPD Baseline or SPD at tumor assessment) is used to classify subsequent tumor assessments for each subject. The SPD at tumor assessment using the irRC for progressive disease incorporates the contribution of new measurable lesions. Each net percentage change in tumor burden per assessment using irRC accounts for the size and growth kinetics of both old and new lesions as they appear. In this study the irRC as defined by the Investigator will serve as the basis of key endpoints for efficacy analyses and guide clinical care.

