#### 1.1.1.1.7 Definition of Index Lesion Response

**Immune-related Complete Response (irCR),** which is defined as complete disappearance of all index lesions. Lymph nodes that shrink to < 10 mm short axis are considered normal.

**Immune-related Partial Response (irPR),** which is defined as a decrease, relative to baseline, of 50% or greater in the sum of the products of the 2 largest perpendicular diameters of all index and all new measurable lesions (ie, Percentage Change in Tumor Burden), in the absence of irCR.

Note: the appearance of new measurable lesions is factored into the overall tumor burden, but does not automatically qualify as progressive disease until the SPD increases by  $\geq 25\%$  when compared to SPD at nadir

Immune-related Stable Disease (irSD), which is defined as not meeting the criteria for irCR or

irPR, in the absence of immune-related progressive disease (irPD)

**Immune-related Progressive Disease (irPD),** which is defined as at least a 25% increase in Tumor Burden (ie, taking sum of the products of all index lesions and any new measurable lesions) when compared to SPD at nadir.

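### Appendix D scores index nodes that shrink to normal inconsistently: the irCR text and the irCR table row disagree, and irPD has no minimum node size

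*Combined protocol and SAP*

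**What the plan says.** All of the following is in Appendix D unless stated.

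- **What counts as normal.** Under 1.1.1.1.7, "Lymph nodes that shrink to < 10 mm short axis are considered normal". The overall irCR text in 1.1.1.1.10 says "All lymph nodes short axes must be < 10 mm".
- **What the table requires.** In the table of 1.1.1.1.10 the only irCR row carries -100% in the column headed "Change in irSPD Tumor Burdon (including measurable new lesions when present".
- **What enters the sum.** Under 1.1.1.1.6, "All index lesions and all new measurable lesions that have emerged after baseline will contribute to the SPD at tumor assessment (irSPD"), with no exception for a node that has become normal.
- **Progression.** irPD in 1.1.1.1.10 includes "At least 25% increase in the SPD of all index lesions over nadir SPD calculated for these lesions". The nadir is the lowest SPD so far, and no minimum absolute increase or size is given. Confirmation at the next assessment is recommended in difficult cases and not required.
- **A competing sentence.** Under 1.1.1.1.3, "Lymph nodes that have a short axis < 10 mm are considered non-pathological and should not be recorded or followed". It stands in the definition of non-measurable lesions and does not say whether it covers an index node that shrinks later.
- **Entry size.** To be measurable, "a lymph node must be at least 15 mm in short axis when assessed by CT scan" (1.1.1.1.2).
- **Role of irRC.** Section 13.3 plans irRC response proportions with 90% intervals in addition to the main response rate. Section 1.1.1.1.6 gives irRC a larger role, in key efficacy endpoints and in care. Section 11.1 assigns response and progression to the ATLL consensus criteria.

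**The concern.** A healthy lymph node does not vanish, so a nodal patient in full response usually still has something to measure. The text allows for this and the table row does not. Best overall response under irRC is to be calculated by the sponsor or a designee from time-point responses and measurements, so whoever derives it must choose a rule that the plan does not supply.

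The second problem follows from the first. If normal nodes stay in the sum, the reference for progression in the best responders is a very small number, and it is the lowest of several noisy readings. A 25% rise over it can come from measurement error alone. At stake are the irCR count, the irRC progression date and whatever is derived from that date.

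**Working it through.** **1. The -100% entry.** Change = 100 x (irSPD at assessment / baseline SPD - 1), where SPD is the sum of the products of the two diameters. Take one index node, 20 x 30 mm at baseline (600 mm²) and 8 x 9 mm later (72 mm²).

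- If nodes under 10 mm are not recorded (1.1.1.1.3 applied at follow-up): 0/600 - 1 = -100%. The table's figure is reproduced.
- If all index lesions contribute (1.1.1.1.6 read literally): 72/600 - 1 = -88%. The irCR row is not met, although the text rule is.

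Other literal cases: 15 x 15 to 9 x 9 mm is 81/225 - 1 = -64%; 30 x 40 to 5 x 5 mm is 25/1200 - 1 = -97.9%. These fall in the irPR range. A node whose long axis persists can fall short of it: 15 x 15 to 9 x 15 mm is 135/225 - 1 = -40%, irSD by percentage, with a short axis that the text calls normal.

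**2. Dropping the node does not settle it.** The nadir becomes 0, and a 25% rise over 0 is undefined. A node going from 9 x 9 to 10 x 10 mm would move the sum from 0 to 100 mm².

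**3. How much growth makes irPD under the literal reading.** A shift d in both diameters gives irPD when (a + d)(b + d) ≥ 1.25ab. For a x b = 8 x 9 and d = 1: 9 x 10 = 90 against 72, exactly +25%. For equal diameters, d = 1 mm suffices up to a = 1/(√1.25 - 1) = 8.47 mm: 7 x 7 gives +30.6%, 8 x 8 gives +26.6%, but 9 x 9 gives +23.5%. A 1 mm shift in one diameter of an 8 mm node gives only +12.5%.

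**4. Chance of a false irPD.** Simulation of 100,000 patients per case. Every node is truly 8 x 9 mm and unchanged. Each diameter has independent normal error, with SD assumed because the documents give none. All scans come after normalisation, the reference is the running minimum, and there is no confirmation. A false call is a rise of at least 25% while every node reads under 10 mm short axis.

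| Residual nodes | SD per diameter | 4 scans | 7 scans |
|---|---|---|---|
| 1 | 0.5 mm | 14% | 33% |
| 1 | 1.0 mm | about 55% | about 86% |
| 1 | 1.5 mm | 64% | 93% |
| 3 | 1.0 mm | about 20% | about 45% |
| 5 | 1.0 mm | 8% | 21% |

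The about figures depend a little on which reading is called the short axis. Taking the smaller of the two gives 56% and 87% with one node and 21% and 47% with three. Holding it to the same diameter gives 54% and 85%, and 18% and 42%. The SD 1.5 mm row uses the same diameter throughout; the five-node row uses the smaller reading.

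Seven scans is the upper end: 46 doses x 2 weeks = 92 weeks, and 92/12 = 7.7, so the node must be normal at the first scan.

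**5. With confirmation.** If the next scan must also be 25% above the earlier nadir, the figures at SD 1 mm fall to about 17% and 48% with one node, and to 4% and 13% with three.

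**The case against.** The strongest reply is that the plan can be read sensibly. Three text rules (index, non-index and overall irCR) accept nodes under 10 mm, against one table cell, and 1.1.1.1.3 can be taken to remove such nodes, which yields -100%. An assessor might well score irCR. This stands in part: a reader might infer that the plan plainly keeps normal nodes in the sum and makes irCR unattainable, and the documents do not support that. The conflict is unresolved. But the reply does not rescue the plan, because removing the nodes leaves a zero nadir, and checking the overall irCR text requires measuring them.

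The simulated rates are also fairly called a worst case. They need few residual nodes and no other burden, an assumed SD, many scans after normalisation, and no confirmation. All of this stands. Confirmation lowers the risk without removing it, and it is only recommended.

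A reader might extend the point to footnote 4 of Section 11.1.4, where progression is a "50% increase from nadir in the sum of the products of measurable disease". That should not be done. The footnote concerns measurable disease, which Section 11.1.2 limits to nodes of at least 15 mm short axis; the ATLL table asks for normal nodes in complete remission and has no -100% entry; and a change would alter the published criteria adopted in Section 11.1.

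Nor do the documents support a claim that the primary response rate is biased. Section 13.1 measures efficacy as CR+PR, and irCR against irPR usually leaves that sum unchanged even within irRC.

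**Conclusion.** The inconsistency is real and confined to Appendix D. On either reading of the node rules something is missing: the literal reading contradicts the irCR text and lets a normal node score as progression, and the alternative leaves progression undefined.

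The arithmetic in steps 1 to 3 needs no assumption beyond the example node sizes. The false irPD rates do: they rest on assumed measurement error and on unchanged 8 x 9 mm nodes. They run from 14% (one node, SD 0.5 mm, 4 scans) to 93% (one node, SD 1.5 mm, 7 scans), and at SD 1 mm they drop to 8% and 21% with five nodes.

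The consequence is a possible under-count of irCR and irRC progression dates that are too early. The irRC CR+PR rate moves only in edge cases such as 15 x 15 to 9 x 15 mm, though with 20 patients one such case is 1/20 = 5 percentage points. Sample size and power are unaffected. It should be corrected before the irRC analysis is programmed, but it does not threaten the main conclusion of the trial.

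**What to change.** Change Appendix D only, as a scoring rule for the irRC analysis:

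1. In the irCR row, replace -100% by: all non-nodal index lesions gone and all nodes under 10 mm short axis.
2. State that index nodes continue to be measured and stay in irSPD after falling below 10 mm, and that the sentence in 1.1.1.1.3 applies to selecting lesions at baseline.
3. State that a percentage rise due only to nodes scores as irPD only if at least one contributing node measures 10 mm or more in short axis.

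Leave footnote 4 of Section 11.1.4 as it is. Where the irRC also guide stopping of treatment, the investigators must reconcile the passages; this point proposes no treatment rule.

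The cost is three sentences and continued measurement of small index nodes. A true nodal relapse may be dated one assessment (12 weeks) later. Some false calls remain when a noisy reading crosses 10 mm: at SD 1 mm, about 1% to 4% with one or three nodes if the smaller reading is the short axis. They are more frequent at SD 1.5 mm: holding the short axis to the same diameter, 19% and 38% over 4 and 7 scans with one node, and 26% and 54% with three. The text should therefore define the short axis as the smaller diameter at each scan.

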#### 13.3 Data Analysis

Data analysis of the study will be descriptive in nature. Demographic and clinical characteristics of the sample, toxicity by grade, as well as tumor response, duration of response, and length of follow-up will be summarized using descriptive statistics. Binomial proportions and their 90% confidence intervals will be used to estimate the response rates of therapy. Binomial proportions and their 90% confidence intervals will also be calculated for the efficacy based on immune response criteria (Appendix D). The Kaplan-Meier method will be used to evaluate the response duration. Analysis of variance methods will be used to evaluate the effects of treatment and time on the viral load measurements, as well as measurements of viral transcripts. The incidence of toxicities will be estimated using the binomial proportion and its 90% confidence interval. A proportional hazards analysis with viral load measures as time dependent covariates will be used to evaluate the effects of treatment and structure the effects of these measures on duration of response. Detailed analysis of correlative studies and biomarkers are listed in Section 9.

The safety and tolerability will be monitored every 2 weeks. All patients who receive treatment with nivolumab will be eligible for safety and tolerability analysis. A Bayesian sequential monitoring method [58] will be used for safety analysis and the stopping rule is defined as  $Pr(\theta>0.10 | data)>0.90$ , where  $\theta$  denotes the proportion of patients who discontinue therapy due to intolerable toxicity. That is, enrollment will be stopped early whenever, given the accumulated observed data, there is >90% probability that the discontinuation of therapy is greater than 10%. Specifically, enrollment will be stopped early if 3 patients discontinue therapy in the first 12 patients, or 4 patients discontinue therapy in the first 19 patients, or 5 patients discontinue therapy before the last patient enrolled. These boundaries were obtained using the free-download software Multc99 (version 2.1) from M.D. Anderson Cancer Center. We assume that the parameter  $\theta$ follows a prior distribution of beta ( $\alpha$ ,  $\beta$ ), with  $\alpha$  and  $\beta$  representing the number of patients discontinuing and continuing therapy respectively.

	Ethnic Categories				T ( )
Racial Categories	Not Hispanic or Latino		Hispanic or Latino		Total
	Female	Male	Female	Male	
American Indian/ Alaska Native	0	0	0	0	0

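### The second overall irPD rule in Appendix D sets index plus new lesions against an index-only nadir, so a patient whose total burden is flat or falling can meet irPD and irPR at the same visit

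*Combined protocol and SAP*

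**What the plan says.** Appendix D, 1.1.1.1.10 gives two size triggers for overall irPD, either of which is enough. The first compares like with like: "At least 25% increase in the SPD of all index lesions over nadir SPD calculated for these lesions". The second is a 25% or greater "increase in the SPD of all index lesions and new measurable lesions (irSPD) over the nadir SPD calculated for the index lesions".

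Elsewhere the appendix uses a different reference:

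- 1.1.1.1.6 defines the burden at each visit: "All index lesions and all new measurable lesions that have emerged after baseline will contribute to the SPD at tumor assessment (irSPD"). It then defines the nadir from that quantity: "the lowest value of the SPD (SPD Baseline or SPD at tumor assessment) is used to classify subsequent tumor assessments for each subject". A post-baseline nadir therefore contains any new measurable lesions present at that visit.
- 1.1.1.1.7 says the appearance of new measurable lesions "does not automatically qualify as progressive disease until the SPD increases by" 25% or more over the SPD at nadir.
- 1.1.1.1.8 describes the nadir as that of index lesions together with any new measurable lesions.
- 1.1.1.1.9 says that new lesions by themselves are not progression.

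Response is measured from baseline, not nadir: "A decrease, relative to baseline of the irSPD of 50% or greater is considered an irPR, in the absence of irCR". It must be confirmed at least 4 weeks later. The overall-response table has one column for percentage change in irSPD and does not say whether the reference is baseline or nadir. No sentence says which label prevails when irPR and irPD are both met.

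Section 13.3 says that binomial proportions with 90% confidence intervals "will also be calculated for the efficacy based on immune response criteria (Appendix D").

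**The concern.** The second bullet puts new lesions in the current value and leaves them out of the reference. Once a patient has carried new lesions through one post-baseline visit, the stable presence of those lesions can register as growth at the next. irRC as set out in 1.1.1.1.7 and 1.1.1.1.9 is meant to avoid that. The effect is stronger the further the index lesions have shrunk, because a smaller index nadir lowers the bar for irPD.

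At stake is whether a first irPR is confirmed. Appendix D has the sponsor or its designee derive best overall response from the time-point responses and measurements. Whoever programs that derivation must choose between two nadirs and between two labels, possibly after seeing the data.

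**Working it through.** The plan states no figure on this point to reproduce. The check applies the rules literally.

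**Rules.** Let B be the baseline SPD, I the index SPD and N the new measurable area at the current visit, and T = I + N (the irSPD). Nadirs come from baseline and earlier visits, because 1.1.1.1.6 applies the nadir to subsequent assessments.

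- irPR (1.1.1.1.10): T ≤ 0.5B, provided irCR is not met.
- irPD, second bullet of 1.1.1.1.10: T ≥ 1.25 × min(B, earlier I).
- irPD, nadir of 1.1.1.1.6 to 1.1.1.1.8: T ≥ 1.25 × min(B, earlier T).

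**Main example.** B = 1000; visits 1 and 2 are both index 200 plus new 100.

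- Visit 1: T = 300. The only earlier value is baseline, so the change is 300/1000 − 1 = −70% on every reference. The label is irPR only.
- Visit 2, against baseline: 300/1000 − 1 = −70%, irPR.
- Visit 2, against the inclusive nadir: 300/300 − 1 = 0%, not irPD.
- Visit 2, against the index-only nadir: 300/200 − 1 = +50%, irPD.

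Nothing changed between the visits, yet the scan that should confirm the irPR also meets irPD.

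**Further cases (B = 100, entries are index + new).**

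| Visit 1 | Visit 2 | From baseline | Over index-only nadir | Over inclusive nadir | Labels under second bullet |
|---|---|---|---|---|---|
| 20+20 | 20+20 | −60% | +100% | 0% | irPR and irPD |
| 20+25 | 20+20 | −60% | +100% | −11.1% | irPR and irPD |
| 20+0 | 20+10 | −70% | +50% | +50% | both, under either nadir |
| 20+0 | 30+0 | −70% | +50% | +50% | both, under either nadir |
| 30+0 | 30+0 | −70% | 0% | 0% | irPR only |
| 30+5 | 30+5 | −65% | +16.7% | 0% | irPR only |
| 20+20 (first post-baseline visit) | – | −60% | −60% | −60% | irPR only |

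In the first two rows the double label comes from the lesion-set mismatch. In the third and fourth the burden really grew from a deep nadir, and both labels apply whichever nadir is used.

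**Range of conflict.** Suppose the index lesions are at their earlier nadir after shrinkage d, so I = (1 − d)B, and N = nB.

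- irPR needs (1 − d) + n ≤ 0.5, so n ≤ d − 0.5.
- irPD by the second bullet needs (1 − d) + n ≥ 1.25(1 − d), so n ≥ 0.25(1 − d).
- The range is non-empty when 0.25(1 − d) ≤ d − 0.5, that is 0.75 ≤ 1.25d, d ≥ 60%.
- d = 70%: new area of 7.5% to 20% of baseline SPD. d = 80%: 5% to 30%. d = 90%: 2.5% to 40%.

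**Which part is due to the mismatch.** Let the visit that set the index nadir also have the lowest irSPD, with new area mB. The inclusive nadir gives irPD only if (1 − d) + n ≥ 1.25[(1 − d) + m], so n ≥ 0.25(1 − d) + 1.25m. Within the range above, the mismatch alone is responsible when n falls below that value. If m = 0, no part of the range is due to it. In the main example d = 80% and m = n = 10%; the inclusive threshold is 5% + 12.5% = 17.5%, so the irPD label is due to the mismatch alone.

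**Grid.** Two-visit records with B = 100, index 0–100 and new 0–50 in steps of 5, visit-1 index above 0, visit-2 total above 0 and below 50: 11,880 records. Both labels apply in 2,662 under the second bullet and 764 under the inclusive nadir, so 2,662 − 764 = 1,898 exist only because of the index-only reference. In 1,706 of the 2,662 the total had not risen since visit 1. These are counts of arithmetic cases, not patient frequencies.

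**Effect on the proportion.** One patient in 20 is 5 points; at the upper planned size of 25 (Section 13.2) it is 1/25 = 4 points.

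**The case against.** The strongest reply has four parts.

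1. **The conflict is conditional.** A reader might infer that any patient with new lesions and a burden down by more than half is both irPR and irPD. The documents do not support that. At the first post-baseline visit the nadir is the baseline, so only irPR applies. Later, the total must reach 1.25 times an earlier index nadir; patients without new lesions and without index regrowth, or with small new lesions, keep irPR alone. This stands.
2. **The mismatch is not the only source of double labels.** A reader might infer that correcting the nadir removes them all. It does not. irPR is set against baseline and irPD against nadir, with no precedence rule, so real regrowth from a deep nadir gives both. This stands, and it widens the repair.
3. **The reach is limited.** A reader might infer that the primary efficacy decision is affected. Section 11.1 bases response on the ATLL consensus criteria, Section 13.1 defines efficacy as CR plus PR, and Section 13.3 adds irRC as a further proportion. The two-stage boundaries in Section 13.2 are unaffected. Appendix D, 1.1.1.1.6 does call investigator irRC the basis of key efficacy endpoints, but that does not change the ATLL-criteria count. An irPR already confirmed also stays the best response. This stands.
4. **Appendix D recommends confirming progression in difficult or mixed cases.** This softens the problem but does not cure it. It is a recommendation, and a repeat scan with unchanged measurements gives the same +50%.

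It could also be argued that 1.1.1.1.10, as the overall-response section, overrides the general definitions. The appendix states no such order, and the bullet would still conflict with 1.1.1.1.8.

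**Conclusion.** Wrong as written. The second irPD bullet contradicts the nadir in 1.1.1.1.6 to 1.1.1.1.8. When new lesions were already present at an earlier post-baseline visit, it can label as irPD a patient whose total burden is down by more than half and is flat or falling, while the same visit meets irPR. The double label is attributable to the index-only nadir only where that earlier total already included new lesions.

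The size is 5 points in 20 on the irRC response proportion and its 90% interval for each patient, not already a confirmed responder, who is scored the other way. The documents give no basis for saying how many patients that would be.

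This rests on taking nadirs from baseline and earlier visits, as 1.1.1.1.6 says, and on irRC being the additional analysis that Section 13.3 describes. The conflict range also assumes index lesions still at their earlier nadir.

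**What to change.** For irRC response classification only, amend Appendix D as follows:

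- Use one nadir in 1.1.1.1.6 to 1.1.1.1.10: the lowest earlier irSPD, with the baseline SPD included. Restate the second irPD bullet as a rise of at least 25% in irSPD over that nadir.
- Align the first irPD bullet. Left alone, it would still call irPD on index regrowth when a fall in new-lesion area has kept irSPD from rising.
- Name the reference for the table's percentage-change column. irPR is judged from baseline and irPD from nadir, so one unlabelled column cannot serve both.
- State which label prevails when irPR and irPD are both met, and whether such a visit can confirm an earlier irPR.

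The cost is a few sentences, settled before the irRC responses are derived, with no new data. Because 1.1.1.1.6 says irRC also guides clinical care, any effect on treatment decisions is for the sponsor to reconcile separately.
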